8.8.2 Primary Efficacy Endpoint

The primary efficacy endpoint is the change from baseline over time in serum phosphorus. Descriptive statistics will be provided for observed value in serum phosphorus, change from baseline and percentage of change from baseline at each visit. The GEE model will be applied to obtain the 95% CIs and p-values. Baseline serum phosphorus measures may be included as covariate in the model.

The proportion of subjects achieving the normal range (3.2-6.1 mg/dL) will be reported. The percentage of time a subject reaches the normal range of serum phosphorus will also be summarized.

In addition, graphs showing the change of serum phosphorus over time will be provided.

8.8.3 Secondary Efficacy Endpoints

8.8.3.1 RGI-C

The efficacy analyses evaluating RGI-C scores will be performed at Week 40 and Week 64. The GEE model will be applied to each RGI-C score type (wrist, knee, global and lower limb deformity) separately to obtain 95% CIs and p-values. Baseline RSS score will be included as a covariate in the model; age may also be included as covariate in the model.

As sensitivity analysis, t test will be performed for RGI-C scores at Week 40 and Week 64. In the case when model assumption is not met, analyses using alternative methods such as non-parametric tests will be performed.

Descriptive statistics for all RGI-C scores will be provided in both continuous and categorical summary. RGI-C responder rate will be calculated. Summary of abnormality at baseline and change in abnormality at Week 40 and Week 64 will also be presented.

8.8.3.2 RSS

The efficacy analyses evaluating change from Baseline of RSS scores will be performed at Week 40 and Week 64. The GEE model will be applied to each RSS score type (wrist, knee and total) separately to obtain 95% CIs and p-values. Baseline RSS score and age may be included as covariate in the model. As sensitivity analysis, t test will be performed for RSS scores at Week 40 and Week 64. In the case when the model assumption is not met, analyses using alternative methods such as non-parametric tests will be performed.

Descriptive statistics for all RSS scores and change from baseline in RSS score will be provided in both continuous and categorical summary.

8.8.3.3 Growth

Growth in standing height/recumbent length and weight will be summarized over time in observed value, Z-score and percentile. Individual subject growth curves will be plotted with CDC growth charts as reference. Historical growth records may be used to evaluate change in growth velocity from pre- to post-baseline.

For standing height/recumbent length Z-score, the GEE model will be applied to obtain 95% CIs and p-values on all scheduled visits. Baseline Z score, age and gender may be included as covariate in the model.

8.8.4 Other Pharmacodynamics Parameters

Other PD parameters such as ALP, 1,25(OH)₂D and urine phosphorus will be summarized descriptively. Summary statistics will be provided for observed value, change from baseline and percentage of change from baseline at each visit. Graphic display will be provided to show the change in PD parameters over time.

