2 STUDY OBJECTIVE(S)

2.1 Primary Objective

The primary objectives of the study are to:

- Establish the safety profile of KRN23 for the treatment of XLH in children between 1 and 4 years old
- Determine the PD effects of KRN23 treatment on serum phosphorus and other PD markers that reflect the status of phosphate homeostasis in children between 1 and 4 years old with XLH

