4.3 Other Efficacy Endpoints

Other efficacy endpoints include

- Change from baseline over time in serum 1,25(OH)₂D and urinary phosphorus
- Change in rickets at Week 40 and 64 as assessed by RGI-C wrist score and knee score
- Change from baseline in RSS wrist score and knee scores at Week 40 and 64

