4.4 Safety Endpoints

General Safety Variables will include the following:

- Treatment Emergent Adverse Events (TEAEs)
- Treatment Related TEAEs
- Treatment Emergent Serious Adverse Events (TESAEs)
- Events to monitor:
 - Injection site reaction (High-Level Term)
 - Immunogenicity

- Hyperphosphatemia
- Ectopic mineralization
- Restless leg syndrome
- Grade 3/4 TEAEs
- TEAEs leading to discontinuation from the study
- TEAEs leading to discontinuation from the study drug treatment
- TEAEs leading to death
- Vital signs and weight
- Physical examinations
- Estimated Glomerular Filtration Rate (eGFR)
- Chemistry, hematology, and urinalysis, including additional KRN23/XLH biochemical parameters of interest (serum calcium, intact parathyroid hormone[iPTH], 25-hydroxyvitamin D [25(OH)D], amylase, lipase, and creatinine; and urinary calcium and creatinine)
- FGF23
- Anti-KRN23 antibody (HAHA) testing and Dose-Limiting Toxicities (DLT)
- Concomitant medications

Ectopic Mineralization Safety Assessments include:

- Renal ultrasound
- Electrocardiogram (ECG)

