⁵ *PHEX* mutation analysis will be performed for all subjects. Potential subjects with prior confirmation of a *PHEX* mutation or variant of uncertain significance in either self or a family member with appropriate X-linked inheritance who meet other eligibility requirements may enroll before screening *PHEX* mutation results are returned.

- 6 Blood and urine to be collected after a minimum fasting time of 4 hours and prior to drug administration (if applicable). Record fasting duration on CRF. Subjects who live more than 45 minutes from the site may stay overnight on the night before the site visit to facilitate fasting sample collection. At Baseline, local lab values will be used to confirm eligibility. Baseline samples will also be sent to the central lab for data analysis. Serum phosphorus may be collected as an unscheduled lab if necessary
- 7 Spot urine collections for urinary calcium, phosphorus, and creatinine
- 8 At site visits, vital sign measurements consist of seated systolic/diastolic blood pressure (BP) measured in millimeters of mercury (mm Hg), heart rate (HR; beats per minute), respiration rate (breaths per minute), and temperature in degrees Celsius (°C). Blood pressure will only be obtained for subjects age 3 or 4 years. Obtain HR, respiration rate, and temperature at the beginning of each visit before any additional assessments are completed. At the Screening Visit BP should be measured 3 times, 30 seconds apart at the beginning of each visit; 3 additional BP measurements, 30 seconds apart, should be obtained at the end of the study visit after all procedures have been performed. At baseline and post-baseline visits, 3 BP measurements 30 seconds apart, should be obtained at the beginning of the study visit.
- 9 At HH visits, vital sign measurements consist of HR (beats per minute) and temperature in degrees Celsius (°C). Obtain at the beginning of each visit before any additional assessments are completed.
- 10 Serum chemistry panels may include PD parameters (i.e., serum phosphorus and ALP), and safety parameters of interest (i.e., calcium) to avoid duplication of testing. Urinalysis will be conducted if possible based on urine volume collected.
- 11 If the development of anti-KRN23 antibodies is suspected in a given subject, samples may be obtained at additional time points on a case-by-case basis, if warranted.

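### Spot-urine phosphorus is analysed with no dilution correction defined, although creatinine is measured in the same sample; hydration adds noise, and the arithmetic mean percent change is pushed upward

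*SAP*

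**What the plan says.** Section 4.3 lists among the other efficacy endpoints "Change from baseline over time in serum 1,25(OH)₂D and urinary phosphorus". Section 8.8.4 fixes the analysis: "urine phosphorus will be summarized descriptively", and "Summary statistics will be provided for observed value, change from baseline and percentage of change from baseline at each visit", plus graphs. Section 8.1 says that continuous summaries include the mean, SD, median and quartiles. Appendix 1 gives descriptive statistics only for the other PD parameters.

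The sample is described in the Appendix 3 footnotes: "Spot urine collections for urinary calcium, phosphorus, and creatinine". Collection conditions are "Blood and urine to be collected after a minimum fasting time of 4 hours", before dosing where applicable. No timed volume or hydration control is stated.

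Urine creatinine appears only as an analyte in its own right: section 4.4 lists "urinary calcium and creatinine" among the safety parameters, and Appendix 2 lists it under spot urine. Section 8.10.2 summarises each laboratory analyte descriptively by time point and counts abnormal results; it plans no percent change. Nowhere does the SAP define a phosphorus/creatinine ratio, a calcium/creatinine ratio, a fractional excretion or a tubular reabsorption measure.

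**The concern.** The phosphorus concentration in an untimed sample depends on how much water the child is passing as well as on how much phosphate the kidney is losing. It can rise or fall between visits with no change in renal phosphate handling. Section 2.1 makes it a primary objective to determine effects on "other PD markers that reflect the status of phosphate homeostasis", and urinary phosphorus is the only urinary measure among those markers. The study has one arm and about 10 children, so no concurrent group shows what hydration alone would do.

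Two effects should be kept apart. Dilution adds noise to every summary of the raw value. In addition, percent change divides by a noisy baseline, so its arithmetic mean is above zero on average even when nothing has changed. The second effect could hide part or all of a true fall in urinary phosphorus.

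**Working it through.** The SAP states no figure on this point, so there is none to reproduce. What follows shows the direction, and the size under stated assumptions.

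**From the SAP:** n about 10 (section 3.5); spot urine with phosphorus and creatinine in one collection (Appendix 3); observed value, change and percent change by visit (8.8.4).

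**Assumed, not in the SAP:** measured concentration = true value × log-normal hydration factor; within-child hydration CV c of 20% to 70%; the same hydration distribution at both visits; correlation ρ between visits of 0 or 0.3. Where residual variation is added, the phosphorus/creatinine ratio has a CV of 20% and normalising removes hydration fully.

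**Step 1: shift in the mean percent change with no true change.** Let s² = ln(1 + c²). The log of the visit/baseline ratio has mean 0 and variance 2s²(1 − ρ), so the expected percent change is exp[s²(1 − ρ)] − 1. With ρ = 0 this is c².

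| Hydration CV | ρ = 0 | ρ = 0.3 |
|---|---|---|
| 20% | +4% | +3% |
| 30% | +9% | +6% |
| 50% | +25% | +17% |
| 70% | +49% | +32% |

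For example, at 70%: s² = ln 1.49 = 0.399. With ρ = 0.3, exp(0.7 × 0.399) − 1 = +32%.

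**Step 2: a true fall of 20%, ρ = 0.** The expected raw mean percent change is 0.8 × (1 + c²) − 1, which is −17%, −13%, 0% and +19% at CVs of 20%, 30%, 50% and 70%.

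**Step 3: the other planned summaries.** With no true change and the same hydration distribution at both visits, the two expected concentrations are equal, so mean absolute change is not shifted, only noisier. In simulation (100,000 trials, n = 10, residual CV 20%), the median percent change averaged +1% to +8% across the same CVs.

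**Step 4: raw value against ratio, same simulation, ρ = 0, no true change.** The raw mean percent change averaged +8%, +13%, +30% and +55% at hydration CVs of 20%, 30%, 50% and 70%, with SDs of the 10-child mean of 14, 19, 34 and 58 points. The creatinine ratio gave about +4%, with an SD of about 9 points. The ratio removes the hydration part, but its own residual noise still biases the mean percent change.

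**Step 5: noise on the log scale.** For an assumed within-child log-SD s of 0.4 to 0.7 (CV = √(exp(s²) − 1), about 42% to 80%) and independent visits, the SE of the mean log change is √2 × s / √10. With s treated as known, the multiplier is 1.96.

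- s = 0.4: SE 0.179, half-width 0.351, range for the geometric mean change −30% to +42%.
- s = 0.7: SE 0.313, half-width 0.614, range −46% to +85%.

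**The case against.** The strongest reply is that the SAP never says it will analyse an uncorrected concentration. Its list in 8.8.4 is open-ended, creatinine is measured in the same collection, and a protocol not shown here may define a ratio. It is true that the uncorrected reading is an inference. But sections 4.3 and 8.8.4 name only urinary phosphorus, and the SAP sets out its other derived measures itself (RGI-C, Z-scores, percentiles). A ratio chosen later would not be pre-specified in this plan.

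The stakes are also modest. This is an other efficacy endpoint, and 8.8.4 and Appendix 1 plan descriptive statistics only, with medians reported alongside means. Section 8.8.1 speaks more loosely of GEE for all efficacy parameters, but neither of those places carries a model for this one. This reply stands and limits the weight of the point.

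Fasting for at least 4 hours may steady intake, but it does not standardise urine dilution. The sizes rest on assumed variation, and between-visit correlation shrinks them; that also stands.

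Lastly, a creatinine ratio is imperfect in children aged 1 to 4 followed for 64 weeks, because creatinine excretion rises with growth. This is a reason to add tubular reabsorption, not to leave dilution uncorrected.

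**Conclusion.** The point holds as a correctable weakness in a descriptive endpoint. As written, hydration is mixed into the plan's only urinary phosphate marker. If dilution varies within a child and is not perfectly correlated between visits, the arithmetic mean percent change is shifted upward. The direction follows from the arithmetic. The size does not come from the SAP: about +4% to +49% for an assumed hydration CV of 20-70% with independent visits, or +3% to +32% at correlation 0.3. The geometric mean change would vary from dilution alone by about −30% to +42% (log-SD 0.4), up to −46% to +85% (log-SD 0.7).

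A reader might infer more, and the documents do not support it:

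- **All urine results are biased upward.** Only the arithmetic mean percent change of phosphorus is materially affected. Mean absolute change is not systematically shifted, and the median moves little.
- **Urine calcium has the same bias.** Section 8.10.2 plans no percent change, so only the noise argument applies.
- **The primary result is at risk.** The primary endpoint is serum phosphorus, and neither it nor any secondary endpoint depends on this measure.
- **A creatinine ratio alone is enough.** Its mean percent change is still biased, by about +4% at the assumed 20% residual CV.

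**What to change.** In sections 4.3 and 8.8.4:

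- Analyse the urine phosphorus/creatinine ratio.
- Add tubular reabsorption of phosphate, 1 − (urine phosphorus × serum creatinine) / (serum phosphorus × urine creatinine), from fasting samples at the same visit. Urine dilution cancels in it.
- Summarise change in the ratio as a geometric mean ratio (log scale) or a median, in place of the arithmetic mean percent change.
- Keep raw concentrations in listings.

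In sections 4.4 and 8.10.2, report the urine calcium/creatinine ratio.

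The cost is SAP wording and a few derived variables; no new sample or visit is needed. Spot urine, serum phosphorus and serum creatinine are all scheduled at Baseline and at Weeks 32, 40, 48, 56 and 64. For earlier visits, compute tubular reabsorption where all the inputs are scheduled together. One small downside remains: the ratio drifts as creatinine excretion rises with growth, which is why tubular reabsorption should be reported beside it.

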8.9 Pharmacokinetics

The PK analysis will be performed on the PK/PD Analysis Set, unless stated otherwise. The descriptive statistics for serum KRN23 will be tabulated. The listing of serum KRN23 will also be provided.

The PK modeling will be detailed in a separate PK analysis plan.

8.10 Safety Analysis

The safety analysis will be performed using the Safety Analysis Set. The safety parameters will include adverse events (AEs) and clinical laboratory, vital sign, physical examination, renal ultrasounds, and electrocardiographic (ECG) parameters.

8.10.1 Adverse Events

Adverse events will be coded by system organ class and preferred term using the MedDRA version 18.1 or the latest version at the time of snapshot/database lock. An AE (classified by preferred term) will be considered as a treatment emergent adverse event (TEAE) if it occurred on or after the first dose and was not present prior to the first dose, or it was present at the first dose but increased in severity during the study.

An overall summary table of AEs will be presented that will summarize the frequency and percentage of subjects who experienced any AE, events to monitor, experienced any TEAE, experienced a treatment-related TEAE, a treatment-emergent SAE, discontinued from study or from study drug treatment due to a TEAE, and experienced an AE leading to death. For this purpose, a treatment-related AE is defined as an AE that is either definitely, possibly or probably related to study medication.

Subject incidence of TEAEs will be tabulated in the following manner: by system organ class/preferred term, by system organ class/preferred term/relationship to study drug, by system organ class/preferred term/severity, and by preferred term for each event to monitor category. In addition, treatment-emergent SAEs, TEAEs leading to study discontinuations and TEAEs leading to death will be tabulated by system organ class/preferred term.

The incidence of injection site reactions will be summarized by study period to assess the trend over time. The summary of incidence over time may also be explored for other events to monitor categories.

Listings will be created for AEs which lead to death, discontinuation of treatment, and SAEs.

8.10.2 Safety Lab Parameters

Clinical laboratory data will be summarized by the type of laboratory test. Descriptive statistics will be calculated for each laboratory analyte at baseline and at each scheduled time point. Shift table for iPTH at each scheduled visit will be provided to assess to the normality over time. The frequency and percentage of subjects who experience abnormal clinical laboratory results and/or clinically significant abnormalities will be presented for each clinical laboratory measurement.

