3.5 Sample Size Considerations

The study will enroll approximately 10 pediatric subjects between 1 and 4 years old, inclusive, with clinical findings consistent with XLH including hypophosphatemia and radiographic evidence of rickets (at least 5 subjects will have a rickets severity score (RSS) at the knee of ≥ 1.5 points at Screening), and a confirmed *PHEX* mutation or variant of uncertain significance. To maintain a level of gender balance, no more than 7 subjects of either gender will be enrolled.

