8.10.5 Renal Ultrasound

Renal ultrasound will be conducted with findings of nephrocalcinosis graded on a 5-point scale by a central reader. The renal ultrasound is read using a pre-defined methodology ([Biomedical Systems Independent Review Manual November 2014](#)). These results will be summarized by time point, a grade shift table summarizing changes from Baseline by time point will also be created.

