8.10.6 Electrocardiogram

Descriptive statistics for ECG parameters (heart rate, RR interval, PR interval, QRS duration, QT interval, and QTc) and changes from baseline values at each assessment time point to the end of study will be presented by. The QTc will be calculated using both the Bazett and Fridericia corrections.

ECG parameters will be summarized by the maximum post-baseline value and maximum change from baseline using the following categories based on FDA guidance (FDA 2015) listed in Table 8.10.6.1.

Table 8.10.6.1: Criteria for ECG Results

ECG Parameter	Categories for Baseline and Maximum Post-Baseline Value	Categories for Maximum Change from Baseline Value
PR Interval	≤ 200 and >200 msec	≤ 20 and >20 msec
QRS Interval	≤ 110 and >110 msec	≤ 10 and >10 msec
QTc Interval	≤ 450 , >450 - ≤ 480 , >480 - ≤ 500 and >500 msec	≤ 30 , >30 - ≤ 60 and >60 msec

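### The laboratory abnormality counts in SAP Section 8.10.2 are not tied to Baseline, visit or direction, so entry abnormalities and new ones share one percentage

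*SAP*

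**What the plan says.** SAP Section 8.10.2 plans three laboratory outputs.

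- By-visit summaries: "Descriptive statistics will be calculated for each laboratory analyte at baseline and at each scheduled time point".
- One categorical table that follows children over time: "Shift table for iPTH at each scheduled visit will be provided to assess to the normality over time". No other analyte is named.
- The abnormality count: "The frequency and percentage of subjects who experience abnormal clinical laboratory results and/or clinically significant abnormalities will be presented for each clinical laboratory measurement". It has no time window, no condition on the Baseline value, no worsening rule and no split by direction.

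Other safety sections of the SAP do set a reference.

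- Section 8.10.1 treats an adverse event as treatment-emergent if "it occurred on or after the first dose and was not present prior to the first dose", or if it was already present and became more severe.
- Section 8.10.3 counts normal and abnormal physical findings by visit.
- Section 8.10.5, renal ultrasound: "a grade shift table summarizing changes from Baseline by time point will also be created".
- Section 8.10.6: "ECG parameters will be summarized by the maximum post-baseline value and maximum change from baseline".

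Section 3.5 describes the roughly 10 enrolled children as having "clinical findings consistent with XLH including hypophosphatemia and radiographic evidence of rickets". Appendix 2 puts phosphorus, ALP, 1,25(OH)2D, iPTH and FGF23 on the safety laboratory list, so the counting rule covers them too.

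**The concern.** Safety is the first of the two primary objectives in Section 2.1. The study is open-label with no control arm, so no background rate can be subtracted, and Baseline is the only internal reference. A count that ignores Baseline gives up that reference.

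Followed literally, a child whose entry abnormality persists adds the same one to the numerator as a child who becomes abnormal on treatment.

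Phosphorus adds a second problem. Low values are the disease. High values are the safety signal: hyperphosphatemia is an event to monitor (Sections 4.4 and 5.9) and part of the dose-limiting toxicity definition (Section 5.10). A child who stays low and a child who goes from low to high fall in the same row.

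The missing window also means that two programmers could follow Section 8.10.2 and produce different tables from the same data.

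**Working it through.** The SAP gives no figure for laboratory abnormalities, so there is none to reproduce. The calculations below only show what the wording allows.

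**Inputs**

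- Children: about 10 (Section 3.5).
- Chemistry, hematology and urinalysis panels (Appendix 3): three on treatment in Table 10.1 and four in Table 10.2 (Weeks 40, 48, 56, 64), so 7 to Week 64. Week 76 makes 8. Column alignment is broken in Table 10.1, so the second panel could be at Week 12 or Week 15. The number of marks is not affected.
- Chance that one value falls out of range with no disease or drug effect: q = 5%, that is, a 95% reference interval. This is an assumption; q = 2.5% is also shown.
- Within-child correlation between panels: assumed, from 0 to 0.9.

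**1. Entry abnormalities**

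Let b be the share of children abnormal at entry. Take p = 30.2% (step 2) as the chance that a child normal at entry is later flagged. If Baseline values are counted, or if every entry abnormality persists to at least one later panel, the expected count is 10 × [b + (1 − b) × p]. The newly abnormal part is 10 × (1 − b) × p.

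| b (assumed) | Counted | Newly abnormal |
|---|---|---|
| 50% | 5 + 5 × 0.302 = 6.5 | 1.5 |
| 80% | 8 + 2 × 0.302 = 8.6 | 0.6 |
| 100% | 10.0 | 0.0 |

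If only post-baseline values count and every entry abnormality resolves before the first panel, the count falls to the right-hand column. The SAP's wording permits anything between the two columns. The table ignores direction: a child going from low to high would be newly abnormal on the high side.

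**2. Chance flags if the count is cumulative**

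For independent panels, P(at least one flag in k panels) = 1 − (1 − q)^k.

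- q = 5%, k = 7: 1 − 0.95^7 = 30.2%, about 3 of 10 children.
- q = 5%, k = 8: 1 − 0.95^8 = 33.7%.
- q = 2.5%, k = 7: 1 − 0.975^7 = 16.2%.

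For correlated panels, with equal correlation between normal values, q = 5%, 7 panels and 400,000 simulated children:

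| Correlation | Any flag over 7 panels | Any flag and normal at Baseline |
|---|---|---|
| 0 | 30.2% | 28.7% |
| 0.5 | 23.0% | 20.0% |
| 0.9 | 11.4% | 6.9% |

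Under independence the right-hand figure is 0.95 × 30.2% = 28.7%. A newly-abnormal rule therefore removes little of the chance part unless values are highly correlated.

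**3. Chance flags if the count is by visit**

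The expected chance rate at each visit is q, the same as at Baseline, whatever the correlation. The 11% to 30% figures do not arise.

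**4. What other output covers**

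| Analyte | Baseline-referenced summary elsewhere |
|---|---|
| Phosphorus | Change and percent change, share in normal range (Section 8.8.2) |
| ALP, 1,25(OH)2D | Change and percent change (Section 8.8.4) |
| iPTH | Shift table (Section 8.10.2) |
| Calcium, creatinine, 25(OH)D, hepatic enzymes, amylase, lipase | None by category; by-visit descriptive statistics and listings only |

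**The case against.** The strongest reply is that the SAP is silent here, not wrong. A reader might infer that Section 8.10.2 prescribes a cumulative count with Baseline values included. It does not say so. The two sentences before the count work by visit, so a by-visit count is a natural reading, and on that reading repeated panels do not inflate the rate. This stands, which is why the cumulative figures are conditional.

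A reader might also infer that a phosphorus row near 100% would be the trial's account of phosphorus. The documents do not support that. Phosphorus is the primary efficacy endpoint with its own baseline-referenced analysis, and high values are picked up as events to monitor and as dose-limiting toxicities. Nor does the SAP say that ALP, iPTH or 1,25(OH)2D are abnormal at entry; it states only hypophosphatemia.

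It would likewise go too far to say that the planned output cannot separate entry abnormalities from new ones. Every analyte has statistics at Baseline and each visit, all data are listed (Section 8.1), and with about 10 children a reader can trace individuals. Still, means and medians do not show which children changed category, and a listing is not a summary.

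Seven panels do not apply to every analyte. If the separate schedule rows govern, iPTH has about 4 on-treatment draws and 25(OH)D about 3, giving 1 − 0.95^4 = 18.5% and 1 − 0.95^3 = 14.3% under independence. Finally, a shift to the worst post-baseline value would keep the repeated-look problem, so it is not proposed.

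What remains is that the count has no stated reference, although the SAP sets one in its other safety sections.

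**Conclusion.** The concern holds in a limited form. Section 8.10.2 defines a laboratory abnormality percentage without reference to Baseline, visit or direction. In a single-arm study with safety as a primary objective, that percentage cannot by itself tell an abnormality carried in from entry from one that arose on treatment. For phosphorus it merges opposite meanings. The gap matters most for calcium, creatinine, 25(OH)D, the hepatic enzymes, amylase and lipase, where no baseline-referenced category table fills it.

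The size depends on readings the SAP leaves open. With half the children abnormal at entry, the count could be anywhere from 1.5 to 6.5 of 10. If it is cumulative, chance flags would be about 11% to 30% per analyte over 7 panels. These figures rest on an assumed 95% reference interval, correlation from 0.9 to 0 and, for the entry illustration, an assumed entry share and independent panels.

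Only descriptive tables are affected, and no test or decision rule uses them. The change is still worth making because it is cheap and bears on a primary objective.

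**What to change.** Revise Section 8.10.2 as follows.

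1. Define the abnormality count as children with a post-baseline value outside the reference range in a direction not present at Baseline. Report low and high separately.
2. Give by-visit frequencies of low and high values for each analyte, with Baseline as the first column. This display is what deals with chance flags over repeated panels; the newly-abnormal rule deals with abnormalities present at entry.
3. Extend the planned by-visit iPTH shift table to calcium, phosphorus, creatinine, 25(OH)D, the hepatic enzymes, amylase and lipase.

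The cost is SAP wording and table programming on data already collected. The downside is a few more descriptive tables for about 10 children. No test, alpha level or sample size changes.
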